5.0 Required Observations

All Pre-study Observations must be done within 14 days of study entry.

Observation	Pre-Study	Day 1 of Cycle 1	Day 15 of Cycle 1	Prior to subsequent cycles 2-12	Prior to subsequent cycles 13-24	End of therapy/Off Study
History, VS, Physical	x	x	x	x	x	x
Performance Status ¹	x	x	x	x	x	x
Toxicity Evaluation			x	x	x	x
Neuro Evaluation	x	x	x	x	x	x
Concomitant Meds	x	x	x	x	x	x
CBCD, Platelets	x	x	x	x	x	x
PT/PTT	x	x	x	x†	x†	x†
CMP w/Phos	x	x	x	x	x	x
Urinalysis ³	x					
Serum Pregnancy ³	x					
MRI-Brain/Spine**	x			Every 3 cycles starting with end of Cycle 3↑	End of Cycle 18 and 24 only†	x
LP/CSF cytology*	x			Every 3 cycles starting with end of Cycle 3 ²	End of Cycle 18 and 24 only ²	x ²
Biology-red & purple top blood samples		x	x			
Data Collection Submission ⁴	x			x	x	x

1:Performance Status=Karnofsky if > 16 y/o or Lansky if ≤ 16 y/o

2: repeat only if cytopathology showed tumor cells at study entry or disease progression

3: Repeat as needed for good clinical care

4: Data Collection should be submitted monthly

†: Repeat PT/PTT only if abnormal after Day 15

↑ Repeat MRI Spine only if not normal pre study

* Lumbar Puncture/CSF cytology is not required if already done within 4 weeks of study entry.

CSF will be obtained prior to initiation of therapy with Poly ICLC. If positive, CSF will be obtained at 3, 6, 9, 12, 18, 24 months after study entry, as well as the time end of therapy/off study.

MRI Brain/Spine should be obtained with and without gadolinium including pre T1, post T1, T2 and flair sequences. Both axial and either coronal or sagittal pre-post gadolinium images should be obtained.

MRI will be assessed at 3, 6, 9, 12, 18, 24 months after starting the therapy (at the end of those cycles), as well as at the time end of therapy/off study or if subject is going off study prematurely.

**MRI spine does not have to be repeated during the study if it was normal pre-study. It should be repeated at the time end of therapy/off study or if subject is going off study prematurely.

A copy of the MRI images on a CD should be sent to the coordinating site.

5.1: Pretreatment Evaluation (must be performed within 14 days of study entry)

- A. History, vital signs and physical examination, including neurologic evaluation and concomitant medication list
- B. CBC, differential, platelet count, PT/PTT
- C. AST, ALT, alkaline phosphatase, albumin, calcium, phosphorus, total bilirubin
- D. BUN, Cr, urinalysis
- E. Disease evaluation with either MRI of brain/spine and CSF cytology. (LP is not required if already done within 4 weeks of study entry).
- F. Serum B-HCG in females of childbearing age
- G. Lansky Play Scale assessment for patients ≤ 16 years of age; Karnofsky score for patients >16 years old. (see Appendix I).
- H. Study entry form/eligibility check list to be filled out prior to starting treatment.

5.2: Evaluation during treatment

- A. Disease evaluation (including MRI), if positive at study entry, every 3 cycles for the first 12 cycles (to be done at the end of the cycle), then every 6 cycles for as long as the subject remains on study. MRI spine does not have to be repeated if it was normal pre-study. Disease status and events form is to be filled every 3 months for the first 12 months and then every 6 months while subject is on study.
- B. History, vital signs, physical examination and concomitant medication list at day 1 and day 15 of cycle 1, and then prior to each cycle (monthly for as long as the patient remains on study).
- C. Labs are to be obtained at day 1 and day 15 of cycle 1, and then prior to each cycle (monthly for as long as the subject remains on study).
 - CBC/differential, platelets
 - Chemistry panel including: AST, ALT, alkaline phosphatase, albumin, calcium, phosphorus, total bilirubin, BUN, Cr
 - PT/PTT at Cycle 1 Day 1 and 15, repeat further only if abnormal
- D. Neurologic assessment at each visit with scoring of overall exam compared to previous exam as follows: No change from previous exam; worsening from previous exam; improvement from previous exam.
- E. Record at each visit if steroids are being given and if dose is same, lower, higher than at previous visit. MRI required if steroid dose increased.
- F. Toxicity monitoring form and Lansky Play Scale assessment for subjects ≤ 16 years of age; Karnofsky score for subjects >16 years old. (see Appendix I) at week 2 and then prior to each cycle.

5.3: Evaluation at the end of therapy or relapsed disease

- A. Disease evaluation (including MRI brain and spine) and lumbar puncture for CSF cytology (required only at time of disease progression) with all studies that were initially positive at study entry
- B. History, vital signs, physical examination, and concomitant medication list
- C. Labs:
 - CBC/differential, platelets
 - Chemistry panel including AST, ALT, alkaline phosphatase, albumin, calcium, phosphorus, total bilirubin, BUN, Cr
 - PT/PTT, if still abnormal
- D. Neurologic assessment with scoring of overall exam compared to previous exam as follows: No change from previous exam; worsening from previous exam; improvement from previous exam.
- E. Record if steroids are being given and if dose is same, lower, or higher than at previous visit.
- F. Toxicity monitoring form and Lansky Play Scale assessment for patients \leq 16 years of age; Karnofsky score for patients $>$ 16 years old. (see Appendix I).
- G. If patient death occurs, fill out death report form.

5.4: Special laboratory specimens

A. Biologic correlates

1. Blood Specimens

Obtain 5ml of peripheral blood in a red top tube at study entry and at day 15 prior to the scheduled dose of the study drug. Separate serum and freeze at -70C in four equal aliquots. Label each specimen with subject's research identifier and date drawn. These specimens will be sent to the lab identified on the next page.

Obtain 10ml of peripheral blood in purple top tube, at study entry and at day 15 prior to the scheduled dose of the study drug. Label each specimen with subject's research identifier and date drawn. These specimens will be sent to [name] laboratory for isolation of peripheral blood mononuclear cells (PBMC). Samples will be shipped to the address listed below.

Serum OAS and interferon α , β , γ levels will be measured by standard ELISA assays. Peripheral blood mononuclear cells (PBMC) will be isolated by ficoll-hypaque density gradient separation and stored as pellets at -80 degrees C. Levels of PKR kinase, phosphorylation state of eIF2 α , and the induction of p21^{Waf-1} will be determined in cell lysates by standard in vitro kinase and Western blot methods using phospho-specific antibodies as described by Williams (1999). This evaluation will provide a surrogate marker for sensitivity of patient's cells to known capacity of poly-ICLC to activate this serine/threonine kinase and to activate the p53 tumor suppressor gene activity.

Total RNA for RNA sequencing or microarray analysis of PBMCs before and after treatment with poly-ICLC will be collected to determine differences in gene expression induced by poly-ICLC as index of somatic response to this agent. This will be compared to patient's clinical response to poly-ICLC.

Peripheral mononuclear cells will also be studied by Fluorescence Activated Cell Sorting to establish an immunophenotypic profile for each sample pre and post treatment with poly-ICLC. Regulatory T cells (Tregs), dendritic cells, mononuclear cells, macrophages, B/T cell subtypes, and pro-anti-inflammatory cytokines can also be analyzed. This will also be tested to determine if these markers can serve as feasible additional biomarkers of disease and response.

2. CSF Specimens (optional)

CSF will be obtained prior to initiation of therapy with Poly ICLC. CSF will be obtained via lumbar puncture as part of clinical staging prior to study enrollment, if not already done within 4 weeks of study entry. CSF cytology will be evaluated for presence of tumor cells by an institutional pathologist using standard methods. Approximately 3 ml of CSF will be requested for proteomic analysis. The CSF will be spun at 400-500 g for 10 minutes to remove cellular contaminants. The first 2 ml of CSF supernatant will be aliquoted into four .500 ml units and frozen at -20 to -80 degrees Celsius to be used for proteomic analysis. Each tube must be labeled with the subject's research identifier, the sample type and the time it was drawn.

The remaining 1 ml of CSF will be aliquoted in 0.2 ml units and frozen at -20 to -80 degrees Celsius to be evaluated for cytokines. Each tube must be labeled with the subject's research identifier, the sample type, site from where the sample was obtained, and the time it was drawn.

All blood and CSF biologic samples should be sent on dry ice, along with a completed biologic specimen transmittal form to [name] laboratory located at the Moores Cancer Center at UCSD. Enrolling practitioners should contact [name] at [contact] to notify him of specimens ready for shipment or pickup and delivery:

[name] PhD
Moores UCSD Cancer Center RM 3312
[name]
University of California, San Diego
La Jolla, CA 92093-0819
[contact]
[contact]

Samples will only be received Monday through Thursday.

B. Laboratory analysis

1. Proteomic Biomarker Evaluation

Criteria for a successful proteomic methodology for identification of a usable biomarker include high throughput, reproducibility and toleration of real world collection and shipping conditions. In addition, such methods must be able to identify differentially expressed proteins in an unsupervised manner as well as provide information about specific proteins of interest. Currently, there is not a single mature technology available to meet all these criteria. Therefore, a combined approach will be employed in this exploratory study to attempt to fit all of these characteristics and improve the body of knowledge about the utility of these strategies.

All these approaches will require concentration of the samples using Centricon 3kD filtration and partial depletion of IgG and albumin (Proteoprep Blue Albumin Depletion kit). Proteins can be precipitated using 15% trichloracetic acid, re-suspended in denaturing buffer and stored at -20 to -80 degrees Celsius until the time of analysis.

The first component of the proteomic approach will employ 2-D gel electrophoresis to separate proteins in two dimensions according to their size and charge. The gels are then scanned and relative positions and intensities are quantitated by pixel reading software. Individual spots are normalized to total signal and proteins that are found to be differentially expressed can be identified by in-gel digestion and MALDI-TOF-TOF mass spectrometry [Clin Chem 2005; 51:2031-2042].

The second approach to employ is LC-MS/MS in combination with stable isotope labeling. The entire sample is subjected to mass spectrometry after trypsin digestion. Individual proteins can be quantitated and identified from the peptides present in the digestion reaction. The protein complements contained in CSF from different disease states can then be compared.

The third component is low mass fingerprinting. Peptides are isolated from the CSF by ultra-filtration. These peptides are interrogated by MALDI-TOF-TOF mass spectrometry and profiles of peaks are generated. Peptide profiles are analyzed by bioinformatics software after signal normalization and informative peaks that distinguish between known disease states are identified. Combinations of informative peaks are compiled and tested against "unknowns" to validate their predictive power.

2. ELISA for confirmation/correlation of target proteins

CSF samples will be evaluated for expression of specific secreted proteins implicated in tumor progression, migration and response to therapy. These target proteins, described above, have well-characterized, commercially available antibodies including VEGF, dFGF, attractin, SPARC and EGF.

3. Interrogation of spinal fluid samples will be performed after investigators have obtained extramural funding to pay for the studies. If compelling evidence for biomarkers other than those described above becomes available as proteomics studies are completed in CSF of children with malignant tumors, inspection for these markers will be performed.

5.5: Pathology specimens (optional)

If the subject has available fixed, frozen and/or cryopreserved tumor tissue from a prior tumor resection upon study entry it will be evaluated for genomics and other biomarkers by study pathologist [name]. Samples should be shipped or picked up and delivered Monday-Friday to:

[name]., Ph.D.
Professor of Pathology, Director of Neuropathology
University of California, San Diego
[name]
La Jolla, CA 92093-0612
[contact]

Additional Consideration

If a patient relapses or second look surgery and/or lumbar puncture is required while the subject is on study, the tissue and/or CSF may be obtained for additional analysis post treatment with Poly ICLC.

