3.2 Inclusion Criteria

3.2.1 Age

Subjects must be between 0 – 21 years of age when enrolled on this protocol.

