3.2.6 Organ Function Requirements

All subjects must have adequate organ function defined below when starting on protocol.

3.2.6.1 Hematologic Function:

- a. Hemoglobin: ≥ 8.0 gm/dl (may transfuse PRBCs)
- b. ANC: $\geq 750/\text{mm}^3$, Must be at least 7 days after last dose of growth factor
- c. Platelet Count: $\geq 50,000$ (transfusion independent; ≥ 7 days from last transfusion)

3.2.6.2. Renal Function defined as:

Creatinine clearance/GFR > 70 cc/min/1.73 m² or

Serum creatinine based on age/gender as follows:

Age	Maximum Serum Creatinine (mg/dL)	
	Male	Female
1 month to < 6 months	0.4	0.4
6 months to < 1 year	0.5	0.5
1 to < 2 years	0.6	0.6
2 to < 6 years	0.8	0.8
6 to < 10 years	1	1
10 to < 13 years	1.2	1.2
13 to < 16 years	1.5	1.4
≥ 16 years	1.7	1.4

The threshold creatinine values in this Table were derived from the Schwartz formula for estimating GFR (Schwartz et al. J. Peds, 106:522, 1985) utilizing child length and stature data published by the CDC.

3.2.6.3 Liver Function:

- a. Total bilirubin \leq 1.5 x ULN for age, AND
- b. SGPT (ALT) < 2.5x ULN
- c. SGOT (AST) < 2.5x ULN

3.2.6.4 Pulmonary Function:

No evidence of dyspnea at rest, no exercise intolerance, and a pulse oximetry \geq 94% if there is clinical indication for determination.

3.2.6.5 Coagulation Function:

Normal PT and PTT at enrollment per institutional range

3.2.6.6 Reproductive Function:

Due to potential teratogenic effects of (poly-ICLC), negative serum beta-HCG in females, and agreement to the use of effective contraception in males and females of childbearing potential, **IS REQUIRED**.

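### Research blood is a fixed 15 ml at entry and again at day 15 for every subject from age 0, with no body-weight limit; the burden is material only in the smallest infants

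*Combined protocol and SAP*

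**What the plan says.** Section 5.4 A.1 gives two separate instructions. The one for serum begins: "Obtain 5ml of peripheral blood in a red top tube at study entry and at day 15 prior to the scheduled dose of the study". For mononuclear cells: "Obtain 10ml of peripheral blood in purple top tube, at study entry and at day 15", again before the dose due that day. The serum tube serves the OAS and interferon ELISAs. The purple-top tube serves PKR, eIF2α and p21, RNA expression and the flow-cytometry profile.

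The schedule in section 5.0 lists both tubes among the required observations, on day 1 and day 15 of cycle 1. The CSF sample carries the label "CSF Specimens (optional" and section 5.5 labels pathology specimens the same way; research blood has no such label. The visible text has no adjustment for age or weight, no maximum, no reduced-volume option and no order between the tubes.

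On who may enter, section 3.2.1 states: "Subjects must be between 0 – 21 years of age when enrolled on this protocol". The creatinine table in section 3.2.6.2 begins with a row for "1 month to < 6 months". Section 3.2.6.1 sets "Hemoglobin: ≥ 8.0 gm/dl (may transfuse PRBCs" as the hemoglobin criterion. Clinical samples share the same visits: section 5.2 states "Labs are to be obtained at day 1 and day 15 of cycle 1", covering blood count, chemistry and PT/PTT, with no volumes given.

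**The concern.** A fixed volume that is trivial in an adolescent becomes a noticeable share of blood volume in a very small infant. Such a child may also enter at the hemoglobin floor. These tubes support secondary marker objectives (1.2.5 and 1.2.6), so any burden they add is avoidable. As the section is written, a site that draws less departs from a required observation and has no guidance on which tube to keep.

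There is a smaller analytic question. Section 9.2.4 uses the baseline and two-week samples and tests changes from baseline, but has no rule for a short or missing tube. If reduced draws occur, they would fall on the smallest children, and the plan should say how their markers are handled.

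**Working it through.** The plan states no total research volume, ml/kg figure or share of blood volume, so there is no figure of its own to reproduce.

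**Inputs from the documents**
- Red top 5 ml and purple top 10 ml, each at entry and at day 15 (5.4 A.1).
- Draws placed on day 1 and day 15, so about two weeks apart (5.0 schedule).
- Lower age limit 0 (3.2.1); hemoglobin floor 8.0 g/dl, transfusion allowed (3.2.6.1).

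**Assumptions, because the documents give neither**
- Body weight 3 to 30 kg.
- Blood volume V of 70 to 90 ml/kg.

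**Volume**
- Per draw: 5 + 10 = 15 ml.
- Both draws: 2 × 15 = 30 ml.

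**Share of blood volume** = ml drawn / (weight × V). At 4 kg, one draw is 15/(4 × 90) = 4.2% to 15/(4 × 70) = 5.4%, and both are 30/(4 × 90) = 8.3% to 30/(4 × 70) = 10.7%.

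| Weight (kg) | One draw, ml/kg | Both, ml/kg | One draw, % | Both, % |
|---|---|---|---|---|
| 3 | 5.0 | 10.0 | 5.6-7.1 | 11.1-14.3 |
| 4 | 3.75 | 7.5 | 4.2-5.4 | 8.3-10.7 |
| 5 | 3.0 | 6.0 | 3.3-4.3 | 6.7-8.6 |
| 7 | 2.14 | 4.29 | 2.4-3.1 | 4.8-6.1 |
| 10 | 1.5 | 3.0 | 1.7-2.1 | 3.3-4.3 |
| 20 | 0.75 | 1.5 | 0.8-1.1 | 1.7-2.1 |
| 30 | 0.5 | 1.0 | 0.6-0.7 | 1.1-1.4 |

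**Where the share becomes notable.** Setting 30/(weight × V) to 10% gives weight = 30/(0.10 × V), or 3.3 kg (V = 90) to 4.3 kg (V = 70). Setting it to 5% gives 6.7 to 8.6 kg. These percentages are only markers on the scale; the documents set no limit.

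**Effect on the day 15 blood count.** The second research draw is at the same visit as that count, so by design only the first 15 ml precedes it. A crude upper bound on the fall assumes full dilution, no regeneration and no transfusion: 8.0 × (1 − 15/(weight × V)). At 4 kg this gives 7.57 to 7.67 g/dl, a fall of about 0.3-0.4. At 10 kg it gives 7.83 to 7.87 g/dl, a fall of 0.1-0.2. The second draw can bear only on later counts.

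All figures cover research blood alone. The safety samples add to them by an amount the documents do not give.

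**The case against.** The strongest reply is that the case is extreme and already governed. Entry requires documented progression or recurrence (3.2.3) and, outside SEGA and certain optic nerve tumors, pathologic confirmation with central review (3.1, 3.2.2), so a 4 kg child will be rare. Section 3.4.2 requires institutional rules to be met and the IRB to approve the protocol. Consent pages are not in the reviewed text, so a volume limit stated there cannot be excluded. Much of this stands, and it keeps the point small. It does not remove it: an approved protocol with fixed volumes still tells sites to draw them, and staff work from section 5.4.

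Four stronger readings are tempting but not supported:
- *Infants in general lose a large share of their blood.* The table shows otherwise: at 10 kg both draws come to 3.3-4.3%.
- *The creatinine rows show that infants are expected.* They show how renal function is judged if one enters. The number among the 23 planned subjects is not given.
- *A child whose site refuses the volume is lost to every marker.* The tubes are separate instructions feeding separate assays, section 9.2.4 tests marker by marker, and nothing excludes a child with one tube. Selective loss of the youngest is possible but cannot be sized.
- *The full 30 ml distorts the day 15 toxicity check.* Only the first 15 ml can.

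Nor do the documents show that the serum tube should always come first. That order would shift the loss to the PBMC markers (PKR, eIF2α, p21) that section 2.2 names as the cellular-response measures.

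**Conclusion.** The point holds in a limited form. Section 5.4 A.1 fixes research blood at 15 ml twice for every subject, without a weight limit, in a trial open from age 0 and from a hemoglobin of 8.0 g/dl. The burden is real at about 3-5 kg, modest by 10 kg and immaterial in older children. The percentages rest on the assumed 70-90 ml/kg and the illustrative weights. How many children are affected is unknown, so neither the overall safety burden nor any loss to the marker analyses can be quantified. The primary endpoint, sample size and two-stage rule do not depend on these samples. This is a cheap improvement, not a flaw in the trial's main inference.

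**What to change.** In section 5.4 A.1, replace the fixed volumes with wording such as: *Up to 5 ml (red top) and up to 10 ml (purple top) at each time point, with total research and safety blood within the per-kg limit of the site's IRB. A reduced or single-tube draw is allowed, and the markers available from it are analysed.* The sponsor should also name which tube is filled first, according to which markers matter most.

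The cost is about two sentences in one section. The downside is that some marker assays, mainly PBMC-based, may be unavailable in the smallest children.

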4.0 Study Treatment

4.1 Treatment Schedule

Children will receive poly-ICLC 20 mcg/kg/dose twice weekly IM (using Monday/Thursday or Tuesday/Friday schedule if possible). The first 2 doses will be administered in the clinic under supervision.

Vital signs will be monitored every 30 minutes for 2 hours after the first dose. For all subsequent doses administered at home, a temperature log will be kept to document the temperature prior to study drug administration and at two separate time points after each of the 8 doses of study drug in cycle 1. One temperature reading will be assessed between hours 2-4 after study drug administration and one temperature reading will be assessed at 12 hours after study drug administration. After cycle 1, temperature will only be monitored on an as needed basis, such as if the subject is not feeling well. Subjects or their parents will be instructed to use a log to record the temperature monitored at home and any fever should be reported to the study team. In some cases, at the discretion of the research team, subject or parent will be allowed, after appropriate teaching, to administer the study drug at home. The study drug will be dispensed to the subject/parent by the research pharmacy. The study drug will be dispensed in vials along with labeled dose syringes in order to minimize errors in dosing.

Total length of treatment will be two years. Each cycle will be 28 days in length. If subjects demonstrate a response to therapy (see section 7.0), treatment may be continued beyond two years at the discretion of the principal investigator and pending drug availability. For statistical analysis of toxicity, subjects will be divided into two separate cohorts (those with NF1 and those without NF1). The subjects in each of these cohorts will be treated and monitored identically throughout treatment.

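### Section 5.4 sends unprocessed whole blood for PBMC isolation on dry ice, so PBMC markers in tubes shipped that way could not be measured by the stated methods

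*Combined protocol and SAP*

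**What the plan says.** Section 5.4 A.1 handles the two blood tubes differently.

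- **Red-top tube.** The site processes it before shipment: "Separate serum and freeze at -70C in four equal aliquots".
- **Purple-top tube.** The instruction is "Obtain 10ml of peripheral blood in purple top tube, at study entry and at day 15 prior to the scheduled dose", followed only by labelling. The tube then goes to the named "laboratory for isolation of peripheral blood mononuclear cells (PBMC). Samples will be shipped to the address listed below".
- **At the laboratory.** PBMC "will be isolated by ficoll-hypaque density gradient separation and stored as pellets at -80 degrees C". PKR, eIF2a phosphorylation and p21 are measured in lysates of these cells, and RNA is analysed before and after treatment. In addition, "Peripheral mononuclear cells will also be studied by Fluorescence Activated Cell Sorting".

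The shipping paragraph, at the end of the CSF part of 5.4 A, covers both kinds of specimen in one rule: "All blood and CSF biologic samples should be sent on dry ice, along with a completed biologic specimen transmittal form". It adds: "Samples will only be received Monday through Thursday". Section 4.1 sets dosing days "using Monday/Thursday or Tuesday/Friday schedule if possible".

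Section 3.1 names two institutions, one in San Diego and one in Atlanta. The receiving laboratory is at the San Diego cancer center.

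**The concern.** Dry ice suits material that is already frozen. It does not suit a tube from which living or at least intact cells must be separated on arrival. A site that follows 5.4 to the letter would freeze the one blood specimen the laboratory needs unfrozen.

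At stake is the PBMC part of objective 1.2.6 and of the association endpoints in section 9.0 c. Section 5.0 schedules biology blood at only two time points, cycle 1 day 1 and day 15. Section 9.2.4 uses baseline levels and changes from baseline. No later draw can stand in, and a pre-treatment sample cannot be retaken once dosing has begun. If tubes carried locally were spared and shipped tubes were not, usable PBMC data would come mainly from one site.

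**Working it through.** No arithmetic underlies the main point. It rests on setting the steps in 5.4 side by side.

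| Specimen | Done at the site | State when sent | Stated transport | Done on arrival | Compatible? |
|---|---|---|---|---|---|
| Red-top serum | Separated, frozen at -70C in aliquots | Frozen | Dry ice | ELISA for OAS and interferons | Yes |
| CSF (optional) | Spun, aliquoted, frozen at -20 to -80C | Frozen | Dry ice | Proteomics, cytokines | Yes |
| Purple-top blood | Drawn and labelled | Liquid whole blood | Dry ice | Gradient isolation of PBMC, lysates, RNA, cell sorting | No |

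**Order of steps.** For purple-top blood, isolation follows shipment, and freezing (pellets at -80C) follows isolation. The dry-ice rule puts a freezing step before isolation.

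**Search for an exemption.** No section exempts the purple-top tube, gives it an ambient or refrigerated condition, or asks the site to isolate or cryopreserve cells first. The shipping paragraph also allows pickup and delivery, but without a separate temperature rule.

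**Premise from outside the documents.** That whole blood frozen without cryoprotectant loses its intact cells is general laboratory knowledge. The plan does not state it, but its own order of steps agrees with it.

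**Markers affected.** PKR, eIF2a phosphorylation and p21 (PBMC lysates), PBMC RNA and the immunophenotype. OAS and the interferons are serum ELISA measurements and are not affected.

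**Subjects affected.** Section 9.1 plans 14 subjects if the trial stops at stage 1 and 14 + 9 = 23 if it does not. With two draws each, that is at most 2 x 14 = 28 or 2 x 23 = 46 purple-top tubes. The documents give neither the split between sites nor how local tubes are carried. The count can therefore lie anywhere from none (if the laboratory corrects the handling) to every subject.

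**Receipt window.** Day 15 is day 1 plus 14 days, hence the same weekday. Assuming overnight transit, which the documents do not state, draws on Monday, Tuesday, Thursday and Friday arrive on Tuesday, Wednesday, Friday and Saturday. Only the first two fall within Monday to Thursday. This matters for the fix, because it binds only when blood travels fresh.

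**The case against.** Several points on the other side stand.

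- **Reach.** A reader might infer that all four biomarker endpoints in 9.0 c are lost. They are not. Each is worded to cover serum, PBMC and/or CSF, so each keeps its serum OAS and interferon component. Objective 1.2.5 is framed around tumor cells, so PBMC are at most an indirect measure of it.
- **Weight.** These are secondary correlative measures. The primary endpoint, the two-stage design, toxicity monitoring and the stopping rules do not use them.
- **Counts.** It is tempting to state a number of subjects lost, but any such figure needs an assumed site share and an assumption that local tubes escape dry ice. The documents support neither.
- **Weekdays.** A reader might see the Monday-to-Thursday window as a second present defect. It is not: samples that travel frozen can be held until the next week, the dosing days apply only where possible, and nothing requires a Thursday or Friday start. In addition, 5.4 places the first draw at study entry while the 5.0 table places it on day 1, so that draw need not fall on a dosing day.
- **Certainty.** The rule says should, not must. Practitioners are told to contact the laboratory when specimens are ready, and the transmittal form, which is not in the documents, may carry tube-specific instructions.

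The contradiction itself remains. A phone call or a form may catch the error, but the only written shipping condition in the protocol is the wrong one for this tube.

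**Conclusion.** The point holds in a limited form. Section 5.4 gives two instructions for the purple-top tube that cannot both work: ship it on dry ice, and isolate intact PBMC from it on arrival. For tubes actually sent on dry ice, the PBMC-based secondary markers could not be measured by the stated methods at either time point. The Atlanta site is the most exposed because it is remote from the laboratory.

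The conclusion assumes that sites follow the shipping sentence as written and that freezing unprotected whole blood destroys the cells needed. Its size in subjects cannot be derived from the documents. It does not extend to serum OAS and interferon, to CSF, or to the primary analysis. Because a lost baseline specimen cannot be replaced, the wording should be corrected before further purple-top tubes are shipped.

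**What to change.** In 5.4, and on the transmittal form if it repeats the rule:

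1. Limit the dry-ice instruction to the frozen serum and CSF aliquots.
2. Give purple-top tubes their own unfrozen condition, for example ambient temperature by overnight courier with isolation on arrival, as confirmed by the receiving laboratory. State whether the same condition applies to pickup and delivery.
3. Since fresh blood must then arrive Monday to Thursday, prefer Monday or Tuesday draws for subjects whose blood is shipped. Section 4.1 already allows these days, so no dose or dosing schedule changes.
4. Record the time from draw to processing for every PBMC sample.

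The cost is one reworded paragraph, a second box per shipment and a start-day preference for shipped subjects. There is also a scientific cost: phosphorylation state and RNA may change in transit, so shipped and locally delivered samples may differ for reasons unrelated to treatment. The recorded processing time lets the analysis examine that difference, but does not remove it.
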